For this high-impact study, we propose to use a stepped wedge cluster randomization design on five VA hospital wards and at UAB Hospital on four hospital wards to compare a mobility program (MP) to usual care (UC) among a cohort of veterans and other patients age ≥ 50 years. We will examine pre- to post-hospital mobility and adverse outcomes including functional decline, nursing home admission, emergency department (ED) visits, hospitalization and death in the mobility program (MP) and usual care (UC) groups in the year after hospital discharge. The primary outcome of mobility will be measured by the UAB Life-Space Assessment (LSA).¹⁰⁻¹³ Secondary measures of mobility will include self-reported ability to walk $\frac{1}{4}$ mile and drive a car, as described by Gill, et al.¹⁴ We will identify patient-specific characteristics that modify the effect of the mobility intervention on post-hospital mobility and adverse outcomes to determine which hospitalized patients are most likely to benefit from this intervention.

C. SPECIFIC LOCATION OF STUDY: Where will the research take place? (When other institutions are involved it may be necessary to secure the approval of their Institutional Review Boards.)

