Descriptive statistics including mean, standard deviations, distribution, maximum and minimum values for the study variables will be calculated. Data will be examined graphically and by summary statistics for outliers and distributional properties (e.g., normality, skewness) that may lead to transformations or nonparametric analyses where indicated.

To analyze differences in LSA while accounting for changes in units over time, we will use a stepped-wedge design (Figure 4, above), a variation of cluster randomization in which each cluster is eventually assigned to intervention.²¹ By beginning with a pre-intervention period and implementing the interventions in ‘steps’ at set times, each unit serves as its own control, with pre-intervention observations used to estimate any underlying long-term or seasonal trends with precision so that effects from the intervention can be distinguished from these ‘secular’ trends. While the standard stepped-wedge design treats time in discrete blocks (the ‘steps’), this trial will be able to provide more robust estimates of secular trends because observations are linked to the date of each patient’s admission, providing a much finer temporal resolution. To understand the secular trends, we will start by examining smoothed plots of LSA over time overall and stratified by unit to identify especially large temporal fluctuations that may indicate unanticipated changes in processes or personnel. We will then model LSA during the time prior to the initiation of the intervention using mixed models,²² to account and test for heterogeneity among hospital units (in both means and trends) and possible nonlinearities. While secular trends must be accounted for in the final models, results from this preliminary analysis will inform whether potential trends can be considered to be linear, and whether all units can be considered to have the same trends over time.

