To test the effectiveness of the intervention on mobility, LSA scores and changes in LSA scores for patients in the control condition will be compared to LSA scores from patients in the intervention condition. Mixed models will be used to examine and compare mean LSA over time with time considered a random effect. An indicator term will be included to denote whether the observation was from the period prior to or after implementation of the intervention. The indicator term will represent whether there was an overall difference in the LSA during the intervention period versus the pre-intervention period, and its statistical significance in the model for each outcome will be the primary test of whether the intervention had a significant effect on LSA. A priori we believe that an exchangeable covariance structure will be most suitable for the data. For the secondary hypotheses, i.e., self-reported outcomes for driving (yes/no) and ability to walk $\frac{1}{4}$ of a mile (yes/no), generalized linear mixed models (GLMMs) that account for repeated measures will be used to compare pre- and post-intervention periods. Given the randomized nature of the study design, adjustment for potential confounders will likely be unnecessary as they are expected to be equally distributed between the groups. However, as noted above, we will confirm that any potential confounders, e.g., age, length of hospitalization, and disease burden score (Cumulative Illness Rating Scale-Geriatrics, or CIRS-G²³) are indeed similar between the pre- and post-intervention periods and, should any not be, we will adjust for them in the statistical models provided they are not deemed to be consequences of the intervention.

To test the effectiveness of the intervention on adverse outcomes, we will use mixed models and GLMMs to model changes in functional decline (ADLs and IADLs), number of ED visits, and number of hospitalizations with an approach similar to the above. To test the effectiveness of the intervention on nursing home admission

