To test the effectiveness of the intervention on mobility, LSA scores and changes in LSA scores for patients in the control condition will be compared to LSA scores from patients in the intervention condition. Mixed models will be used to examine and compare mean LSA over time with time considered a random effect. An indicator term will be included to denote whether the observation was from the period prior to or after implementation of the intervention. The indicator term will represent whether there was an overall difference in the LSA during the intervention period versus the pre-intervention period, and its statistical significance in the model for each outcome will be the primary test of whether the intervention had a significant effect on LSA. *A priori* we believe that an exchangeable covariance structure will be most suitable for the data. For the secondary hypotheses, i.e., self-reported outcomes for driving (yes/no) and ability to walk ¼ of a mile (yes/no), generalized linear mixed models (GLMMs) that account for repeated measures will be used to compare pre- and post-intervention periods. Given the randomized nature of the study design, adjustment for potential confounders will likely be unnecessary as they are expected to be equally distributed between the groups. However, as noted above, we will confirm that any potential confounders, e.g., age, length of hospitalization, and disease burden score (Cumulative Illness Rating Scale-Geriatrics⁵⁷) are indeed similar between the pre- and post-intervention periods and, should any not be, we will adjust for them in the statistical models provided they are not deemed to be consequences of the intervention.

To test the effectiveness of the intervention on adverse outcomes, we will use mixed models and GLMMs to model changes in functional decline (ADLs and IADLs), number of ED visits, and number of hospitalizations with an approach similar to the above. To test the effectiveness of the intervention on nursing home admission and death, we will use Cox proportional hazards models

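### The Aim 1 LSA model gives the day-1 LSA no covariate role, and patient-level adjustment depends on a balance check with no criterion

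*Protocol*

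**What the plan says.** The Protocol's Background states: "The primary outcome of mobility will be measured by the UAB Life-Space Assessment". Protocol Table 2 lists the LSA among the assessments for the first study day, and Tables 7 to 9 repeat it at months 1-6, 9 and 12, which makes eight follow-up values.

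The Analytic Approach, worded alike in both documents, commits the final LSA model to an intervention indicator, time as a random effect, an exchangeable covariance and secular-trend terms. The last are unconditional: "secular trends must be accounted for in the final models". Heterogeneity among units is examined and accounted for. Under Aim 1, "LSA scores and changes in LSA scores for patients in the control condition will be compared to LSA scores" from intervention patients, and of the indicator the plan says that "its statistical significance in the model for each outcome will be the primary test of whether the intervention had a significant effect on LSA".

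On patient-level covariates, Aim 1 says that "adjustment for potential confounders will likely be unnecessary as they are expected to be equally distributed between the groups". The plan will confirm that potential confounders "are indeed similar between the pre- and post-intervention periods", and if any are not, "we will adjust for them in the statistical models provided they are not deemed to be consequences of the intervention". The examples given are age, length of hospitalization and the CIRS-G score. The SAP repeats the rule with the same proviso, "provided they are not deemed to be consequences of the intervention". Neither document defines similar or deemed. Pre-admission LSA is named only under Aim 2, as a possible effect modifier.

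**The concern.** A baseline value of the outcome is usually among the strongest predictors of its later values. Here it is already scheduled for collection, yet it could enter the Aim 1 model as a covariate only if someone added it to the open list and then judged it dissimilar between periods, by a criterion that is not written down.

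The stated reason for not adjusting is also weaker than in an individually randomised trial. Under Randomization, the Protocol randomises the order in which five VA and four UAB wards cross over. Under Screening, Recruitment & Consent, patients are approached one at a time after admission to a ward whose condition is already set. Chance imbalance with nine wards, or selective recruitment, could leave the conditions different in pre-hospital mobility. A raw comparison of pre- and post-intervention periods also mixes condition with calendar time. That weakens the check, but not the treatment comparison, which models secular trends.

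At stake are the precision of the primary estimate, some protection against baseline imbalance, and a covariate set fixed before results are seen. Length of hospitalization is an awkward candidate in any case, because it is measured after assignment.

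**Working it through.** **The plan's own figures.** Protocol, Sample Size Calculations: 206 patients, 9 units, ICC 0.004.
- Design effect = 1 + (206/9 - 1) x 0.004 = 1.0876, and 206/1.0876 = 189.4, against 190 stated.
- 206/0.80 = 257.5, which rounds to the 258 enrolled.
- The power of over 90% for 10 points cannot be reproduced, because neither document gives an LSA standard deviation or within-patient correlation. Nothing below shows that 190, 206 or 258 is wrong.

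**Formulas.** Let rb be the baseline-to-follow-up correlation and rf the correlation between follow-up visits, with m = 8 complete visits and equal standard deviations (all assumptions except the visit count). In units of the single-visit variance, for the patient's mean follow-up LSA:
- unadjusted level: V = (1 + 7rf)/8
- change from baseline: V + 1 - 2rb
- baseline as covariate: V - rb²

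**Baseline less correlated than visits are with each other**, which is plausible when an acute admission intervenes:
- rf 0.7, rb 0.3: V = 0.7375; adjusted 0.7375 - 0.09 = 0.6475; ratio 87.8%
- rf 0.6, rb 0.5: V = 0.65; adjusted 0.65 - 0.25 = 0.40; ratio 61.5%

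The standard error is then 94% to 78% of unadjusted.

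**One common correlation:**

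| Correlation | Level | Change | Adjusted | Adjusted/level | Adjusted/change |
|---|---|---|---|---|---|
| 0.4 | 0.475 | 0.675 | 0.315 | 66% | 47% |
| 0.5 | 0.5625 | 0.5625 | 0.3125 | 56% | 56% |
| 0.6 | 0.65 | 0.45 | 0.29 | 45% | 64% |
| 0.7 | 0.7375 | 0.3375 | 0.2475 | 34% | 73% |

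Adjustment has smaller variance than either form named in Aim 1. With 5 visits instead of 8, the adjusted/level ratios are 69%, 58%, 47% and 36%.

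**Does this survive the stepped wedge?** Figures 4 and 4A give 5 x 7 + 4 x 6 = 59 ward-periods, of which 20 + 14 = 34 are under the mobility program. Generalised least squares was run with 206 patients spread equally, ward variance 0.004 of the single-visit variance, site terms and four forms of secular trend (common linear, common quadratic, site-specific linear, site-specific periods). The adjusted/unadjusted variance of the treatment effect was 67.7-67.9%, 57.1-57.4%, 46.3-46.6% and 35.4-35.6% at common correlations 0.4 to 0.7. It was 88.2% for (rf 0.7, rb 0.3) and 62.8-63.0% for (rf 0.6, rb 0.5). The gain therefore hardly depends on the trend form. In simulations of 3,000 runs each, both estimators were unbiased (mean/true 0.993-1.017).

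**Protection against imbalance.** A 5-point baseline difference between conditions would move the unadjusted level estimate by 5 x rb, that is 1.5 points (rb 0.3) to 3.5 points (rb 0.7), against the planned 10. The documents report no such difference.

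**Level or change?** Change at each visit is follow-up LSA minus baseline LSA. If baseline is already a covariate, subtracting it from the outcome lowers its own coefficient by exactly 1 and leaves the intervention coefficient and the residuals unchanged. Both forms then give the same treatment effect.

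**The case against.** The strongest reply is that this is a preference for efficiency: the planned model with secular-trend terms is valid, and no contradiction has been shown. That stands, and it limits the point to precision and prespecification.

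Three further replies stand in part.
- The list of confounders is open, so an imbalanced baseline LSA could be adjusted for under the existing rule. It could, but only through a check with no criterion, and the precision gain does not depend on imbalance.
- Baseline is not wholly unused in Aim 1, because changes in LSA are compared and the aim speaks of recovery to pre-hospital mobility. A change score is not covariate adjustment, however, and it is less precise at every correlation tabulated.
- The common-correlation figures are favourable, since they ignore the intervening illness and incomplete visits. The 88%-62% range is the more cautious one.

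A reader might also go further than the documents allow:
- That no adjustment of any kind is fixed in advance. Secular trends are modelled unconditionally; only patient-level covariates depend on the check.
- That the planned test or the balance check inflates type I error. Nothing here shows that.
- That the day-1 LSA would be a ninth outcome row and dilute the effect. No passage proposes this, and the sample-size text sets the target in the year after discharge.

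**Conclusion.** The concern holds as a matter of precision and prespecification, and the change should be made. The Aim 1 LSA model gives the day-1 LSA no covariate role, and patient-level adjustment rests on an undefined similarity check whose rationale is weak when only the crossover order of nine wards is randomised. The direction of the gain is secure for any non-trivial baseline correlation. Its size is illustrative, because it rests on assumed correlations, equal standard deviations and complete visits: 88%-62% of the unadjusted variance under the cautious assumptions, 66%-34% under a common correlation of 0.4-0.7, and 47%-73% of the change-score variance over that same range. Covariate adjustment reduces bias from selective recruitment but does not remove it.

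**What to change.** In both documents:
1. Include baseline LSA as a fixed covariate in the primary LSA mixed model regardless of observed balance, alongside the planned unit and secular-trend terms, with only post-discharge LSA as outcome rows. No choice between level and change is then needed.
2. Drop the balance check as the trigger for this adjustment.
3. Remove length of hospitalization from the candidate covariates, because it is measured after assignment.
4. Impute missing baseline LSA under the existing multiple-imputation plan.
5. Date the change.

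The cost is wording and slightly more analysis work, with no new data and no change to the sample size. Timing is the real drawback. The periods in Figures 4 and 4A end on 12/31/19, so 12-month follow-up would end at about 12/31/20. The 48 months allowed for assessments, counted from 1/18/17, end on 1/18/21. Both precede the protocol date of February 5, 2021, so follow-up was probably complete by then. If outcomes have already been compared by condition, label the adjusted model as added later and report it beside the planned one.

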DETAILED RESEARCH PROTOCOL

February 5, 2021

A. PURPOSE: *State briefly the purpose of the study; usually this will include the hypothesis, which is to be tested.*

Many older adults experience increased difficulty moving about their communities and performing one or more of their basic activities of daily living (ADLs) after undergoing a hospitalization. The purposes of this study are (1) to test the effectiveness of a mobility intervention, compared to usual care, on change in mobility after hospitalization; (2) to determine the impact on one-year outcomes (such as nursing home placement); and (3) to identify which patients benefit the most from the intervention. Ultimately, our goal is to improve recovery after hospitalization and reduce disability in hospitalized patients.

B. BACKGROUND: *Describe past studies and, if relevant, experimental or clinical findings which led to the plan for this project. This must be succinct and comprehensible without extensive reference to other material. A few pertinent references may be cited. In some cases -- e.g., as in cases where earlier studies have produced conflicting evidence -- it will be necessary to cite these studies and explain how it was decided to rely on one side or the other. For studies designed to compare or evaluate therapies, there should be a statement of the relative advantages or disadvantages of alternative modes of therapy. This section should ordinarily be less than one page long; however, when necessary it may be longer.*

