If the LAR is first contacted by visiting the patient's room, then consenting staff will describe the study to the LAR and the patient; if both the LAR and the patient express interest, then the screening process will proceed, as described above.

Identification, contacting, and consenting of potential UAB participants' LARs will follow UAB procedures and guidelines.

Figure 1. Screening Flowchart (BVAMC)

[figure not shown]

TABLE 1
Screening Procedures

Procedure	Length of Time Required of Participants	Frequency of Repetition
EMR review	0 minutes (performed by staff)	Once
Screening interview with medical team	0 minutes (performed by staff)	Once
Mini-cog	5 minutes	Once
Confusion Assessment Method (CAM)	<1 minutes	Once
LAR Identification, as necessary	0 minutes (performed by staff)	Once
Ambulation question	<1 minutes	Once
Progressive functional assessment (sit, stand)	5 minutes	Once
Total	<12 minutes	

In-Hospital Procedures

Baseline

Baseline Assessments: After consent, a number of baseline assessments will be administered by study staff using standard testing procedures. These assessments may be administered over two or more sessions: One set of assessments is to be administered on Day 1 of the study and takes a little more than 20 minutes to complete; the second set maybe be completed at any time during hospitalization, and takes about 25 minutes to complete. (See Tables 2 and 3). Study staff will be sensitive to the participant's comfort level, and may postpone or eliminate any assessments if the participant expresses fatigue. Staff will also collect demographic information, as well as contact information for post-discharge assessments.

Depression Assessment: Patients will be administered the Patient Health Questionnaire (PHQ) – 2, which is a 2-question screening tool for depression.¹⁸ Surrogate responses will not be solicited for this assessment. A positive answer to either question is considered a positive screen and will lead the interviewer to complete the PHQ-9.¹⁹ Scores for PHQ-9 range from 0 – 27, with higher scores indicating higher levels of depression. If a patient is noted to have a PHQ-9 ≥ 11 , indicating moderate depression, the patient's BVAMC or UAB physician will be notified by study staff.

TABLE 2
Baseline Assessments, Part 1: to complete on first day in the study

[figure not shown]
Procedure	Length of Time Required of Participants	Frequency of Repetition

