Condensed Memorial Symptom Assessment Scale (CMSAS)	5 minutes	Once
Katz ADL	3 minutes	Once
Lawton IADL	3 minutes	Once
UAB Life-Space Assessment	5 minutes	Once
Gait speed	5 minutes	Once
Step count monitoring (via StepWatch)	0 minutes (worn while in hospital)	Continuous during hospitalization
Total	21 minutes	

TABLE 3**Baseline Assessments, Part 2: to complete prior to hospital discharge**

Procedure	Length of Time Required of Participants	Frequency of Repetition
Ability to walk/drive	1 minute	Once
Fall history (previous 4 weeks)	1 minute	Once
ED visit & hospitalization history (previous 6 months)	1-6 minutes	Once
PHQ-2 (& PHQ-9, as appropriate) (depression screening tool)	2 – 6 minutes	Once
Lubben Social Network Scale	7 minutes	Once
EQ-5D-3L (quality of life index)	5 minutes	Once
Total	17-26 minutes	

Mobility Monitoring: The StepWatch® mobility monitor by Modus Health is a small (70 x 50 x 20 mm) waterproof, self-contained accelerometer pedometer that is attached loosely to the ankle via a Velcro strap and captures number of steps taken and when the steps were taken.²⁰ A StepWatch® pedometer will be applied to the ankle and will be worn for the duration of the in-hospital portion of the study by all participants. All patients in the study will wear a StepWatch to allow comparisons of mobility achieved by both the Mobility Program (MP) and Usual Care (UC) groups. Our team has extensive experience with the StepWatches, having used the device in our previous VA Merit study at the BVAMC. Flyers with the study's pager number will be placed on or near the whiteboard located in all patient rooms, and nursing will be informed of the patient's participation in the study and asked to call study staff if there are any questions about the pedometers. The pedometers will be removed as needed if they interfere with routine care, such as MRIs or other procedures.

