MP patients will participate in a program of progressive walking and transfer training up to three times a day, seven days a week (as staffing allows) throughout their hospital stays. MP participants will begin with assisted sitting, then standing, progressing to weight shifting and stepping in place, and then to walking as tolerated. The level of mobility recommended to the MP participant by study staff will be dependent on the individual participant and will incorporate the activities patients were deemed able to do independent of cueing or assistance during each walking session. For example, if a participant could stand at the bedside independently, but required standby assistance for walking, the participant would be encouraged to sit on the side of the bed for meals and stand up beside the bed for 3-5 minutes every two hours as able. To assure participant safety, participants will be instructed not to attempt to transfer or walk without nursing assistance if deemed to be dependent in these activities. The participant and study staff will set daily goals regarding the amount of time the participant will aim to spend out of bed and what level of activity the participant will work on independently. For example, a participant may decide that s/he would like to try to walk to the nurse’s station or to the elevators and that activity would be attempted with the help of study staff. We anticipate that each session will take 15 - 20

minutes; the overarching goal is to progress the participant toward walking as tolerated. A rolling walker or rollator will be provided for walking as needed. This ambulatory device may be left in the room if participants wish, and if they demonstrate that they are able to use the device safely and independently.

During each walk, participants will be asked to rate their exertion using the Perceived Exertion Index (PEI), a simple rating scale ranging from 1 (not tired at all) to 10 (maximal fatigue), in order to take into account the effort and fatigue they may experience while walking. They will be encouraged to walk at a pace that is comfortable. If they indicate that their PEI is higher than 6, they will be asked to stop and rest.

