While MP participants will be encouraged to walk during each study visit, they may refuse any or all sessions. Study staff will attempt to make several visits for each scheduled walk. If a participant is away at a test or procedure, or busy with another healthcare provider, staff will return at a later time to walk with the participant.

Usual Care Group (UC):

UC participants will receive three times a day "friendly visits," seven days a week as staffing allows, to control for the daily attention that MP patients receive. The "friendly visits" will be approximately 15 - 20 minutes in length. Like the MP group, the UC group will wear a StepWatch throughout their hospital stay. These data will be used to document the amount of mobility attained by the UC group, but will not be shared with UC patients. If a participant is away at a test or procedure, or busy with another healthcare provider, staff will return at a later time to visit with the participant. Like MP participants, UC participants may refuse any or all visits.

Both MP and UC Groups:

Additional data collected for both groups will include daily physician mobility orders, as well as physical barriers to patient mobility such as IVs, oxygen tubes, etc. Also, as noted earlier, all participants will continue to wear the StepWatch, except in the unusual event that it should interfere with care (such as MRIs), or if the participant should request its removal.

A questionnaire, the Acute Care Mobility Assessment (ACMA), has been developed for use at the bedside as an assessment of mobility. In a small pilot study at the Birmingham VAMC, we compared results from wireless mobility monitors to patient's and nurses' ACMA scores and found a correlation of 0.62 for both patients and nurses. We wish to continue our validation of this simple instrument in conjunction with usage of the StepWatches. All patients will complete this 5-minute assessment each day they are in the hospital.

TABLE 4
Daily while in Hospital: Mobility Program (MP) Group

Procedure	Length of Time Required of Participants	Frequency of Repetition
Mobility session (walks w/ goal setting & safe ambulation review)	20 minutes	Up to 3x/day
Acute Care Mobility Assessment (ACMA)	5 minutes	1x/day
Perceived Exertion Index	<1 minute	during walks, up to 3x/day
Daily mobility orders & barriers	0 minutes (performed by staff)	1x/day
Step count monitoring (via StepWatch)	0 minutes (worn while in hospital)	Continuous during hospitalization

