and death, we will use Cox proportional hazards models to compare the time from hospital discharge to the time to event between the MP and UC groups, adjusting for potential covariates. Due to the potential interrelationship between risk of nursing home admission and risk of death, competing hazards will be used to model the time to occurrence of the first event. Right censoring of participants will occur with dropout due to any reason (death, loss to follow-up, conclusion of the study period, etc.). Multiple imputation techniques will be used to offset potential bias due to missing predictors in the models.

AIM 2: To identify characteristics which modify the effect of the mobility intervention on recovery to pre-hospital mobility status or better and reduction of adverse outcomes in the year after hospitalization.

Potential effect modifiers include pre-admission ADL and LSA, cognitive function, level of in-hospital mobility, depressive symptoms, and social support. For continuous variables, e.g., activities of daily living score, overall distributions will be reviewed and categorized as low, medium and high based on tertile cut-points. To test for significant effect modification, single second level interaction terms, combining pre-/post-intervention indicators with potential effect modifiers, will be added to mixed models. Resulting F-tests for the interaction terms will be reviewed and p-values <0.05 identified as significant. Examination of potential effect modifiers based upon their tertile groupings not only allows for the identification of significant factors but also has the added benefit of examining factor's dose effect, providing additional internal validity to the analysis.

F. ECONOMIC CONSIDERATIONS: *Describe any material inducements that will be offered to subjects in return for their participation: e.g., direct payment, free services, etc. Describe any schedule of payment to subjects based on their complete or partial participation. Will early withdrawal from the study result in a reduced payment? Does it make a difference whether it is the subject or the investigator who decides to terminate the subject's participation? Explain any bonus a subject may receive for completion of the study. These partial or bonus payments must also be explained in the consent form.*

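### Aim 2's in-hospital mobility modifier has no stated measure or time window; taken over the stay it is a post-assignment variable, and its tertile contrasts are not randomised comparisons

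*Protocol*

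**What the plan says.** The Aim 2 text is the same in the protocol and the SAP: "Potential effect modifiers include pre-admission ADL and LSA, cognitive function, level of in-hospital mobility, depressive symptoms, and social support". Continuous modifiers are cut at tertiles of the overall distribution. Each is crossed with the intervention indicator in a mixed model, and the interaction F-test is read at p < 0.05. Both documents add that the tertile approach shows a factor's "dose effect, providing additional internal validity to the analysis".

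The protocol collects several measures of mobility in hospital:

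- **StepWatch**, worn throughout the stay "to allow comparisons of mobility achieved by both the Mobility Program (MP) and Usual Care (UC) groups" (Mobility Monitoring).
- **The Acute Care Mobility Assessment (ACMA)**: "All patients will complete this 5-minute assessment each day they are in the hospital" (Both MP and UC Groups).
- **Gait speed**, on the first study day (Table 2) and at discharge (Table 6).

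Aim 2 is tied to none of these, and no summary or window is given. Over the same days, "MP patients will participate in a program of progressive walking and transfer training up to three times a day" (Mobility Program Group). Assignment follows the ward's status at admission (Analytic Approach).

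Aim 1 has a guard for covariates that differ between periods: "we will adjust for them in the statistical models provided they are not deemed to be consequences of the intervention". Aim 2 has no equivalent for modifiers.

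**The concern.** An effect modifier supports a randomised subgroup comparison only if the intervention could not have changed it. Mobility over the stay fails that condition, because raising it is the program's direct aim. If the program works, some MP patients in the top tertile would have been in the middle one under usual care. Within a tertile the MP patients are then, on average, frailer than the UC patients beside them. Any factor that drives both in-hospital mobility and later LSA, such as severity of illness, distorts the comparison.

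The third purpose of the study is "to identify which patients benefit the most from the intervention". A value known only after the program has run cannot be used to choose patients for it. The tertile effects could also mislead as estimates even when every patient gains equally. The claim that tertiles add internal validity does not hold for a variable of this kind.

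The Aim 1 guard concerns covariates, so Aim 2 does not contradict it. It does show that the authors apply the principle in one place and not in the other.

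**Working it through.** **Timing.** Set side by side, the sections quoted above fix the order: ward assignment at admission, then enrolment, then sessions up to three times a day alongside StepWatch and ACMA. No section restricts the modifier to a value taken before the first session, and none labels the analysis as mediation. Strictly, any in-hospital measure comes after assignment. Only one taken before the first session is free of the sessions' effect.

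**No plan figure for this point.** The documents give no number to reproduce here. The sample size used below does reproduce: the design effect is 1 + (206/9 − 1) × 0.004 = 1.0876, and 206/1.0876 = 189.4, against the stated 190.

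**Illustrative model.** The documents do not give the SD of LSA, the link between in-hospital mobility and LSA, or the rise in mobility under MP. These are assumed.

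- Mobility: M = aT + U + 0.7e, where T = 1 for MP, U is a health factor (higher is healthier) and e is noise. The SD of M under UC is √(1 + 0.49) = 1.22.
- Outcome: Y = 10T + cU + residual. The true benefit is 10 points for everyone, with no modification and no mediation.
- a = 0.5 or 1.0, which is 0.5/1.22 = 0.41 or 1.0/1.22 = 0.82 UC SDs of mobility. c = 8 or 12 LSA points per SD of U.
- Per-visit LSA SD of 21.2, the value at which 95 per arm and one visit give 90% power for 10 points.

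**Hand check.** If M were held fixed linearly, the MP effect would become 10 − ac/1.49. This gives 7.3, 6.0, 4.6 and 2.0 for (a, c) = (0.5, 8), (0.5, 12), (1, 8) and (1, 12). Tertiles hold M only roughly, so the middle-tertile effects should lie slightly above these values, and they do.

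**Stepped-wedge simulation.** 206 patients, 9 wards, switch dates from Figures 4 and 4A, ICC 0.004. Assumed: 40% of patients from UAB, a linear trend of 5 points over the study, within-patient correlation 0.6, and the complete mean of 8 visits. The model had ward effects, linear time, T, pooled tertile and T × tertile, with 4,000 trials per setting.

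| a | c | Low / middle / high effect | F-test rejects |
|---|---|---|---|
| 0.5 | 8 | 8.1 / 7.7 / 8.2 | 5.4% |
| 0.5 | 12 | 7.1 / 6.4 / 7.2 | 5.3% |
| 1.0 | 8 | 6.2 / 4.9 / 6.0 | 5.3% |
| 1.0 | 12 | 4.2 / 2.5 / 4.0 | 5.6% |
| 1.0 | 0 | 10.1 / 9.9 / 10.2 | 5.0% |

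- With the pre-session value U + 0.7e as the modifier, every tertile effect is 9.9 to 10.0 and rejection is 4.5 to 5.4%.
- The overall MP effect, without tertiles, is 9.9 to 10.1 in these settings.
- One tertile estimate has a sampling SD of 4.6 to 6.0 points, so the bias is about 0.3 to 1.6 of that SD.
- With a weaker shared cause, c = 4, a large 1:1 sample gives 9.0 / 8.7 / 9.0 (a = 0.5) and 8.1 / 7.5 / 8.1 (a = 1.0).

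**Uneven gains.** A separate simpler simulation used 206 patients 1:1, LSA SD 25, a mobility–LSA correlation of 0.5 and an average rise of 0.5 SD, with larger gains in the least mobile. The tertile effects were 1.0 / 2.2 / 6.7. The F-test rejected in 9.1% of trials with no true modification, against 5.7% for the pre-program modifier.

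**Mediation.** If the benefit runs wholly through mobility (a = 1.0, no shared cause), the tertile contrasts are 2.7 / 0.7 / 2.8. They have moved toward a direct effect, which is a different estimand, and this is not counted as bias.

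**The case against.** Five points can be made for the plan.

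1. **The reading is inferred.** The protocol speaks of patient-specific characteristics, and a first-day measure such as gait speed would fit the wording. This stands: what is certain is that the variable is undefined, and the bias is conditional on the window chosen. Even so, the neighbouring ADL and LSA items are expressly pre-admission and this one is not.

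2. **The assumed link to severity may be strong.** With an SD of 21.2 and a within-patient correlation of 0.6, the between-patient variance is 0.6 × 21.2² ≈ 270. Then c = 12 has severity explaining 144/270 = 53% of it, and c = 8 explains 64/270 = 24%. The plan also analyses change in LSA, which could remove part of the shared cause. If that halved c, the first setting would become about 9.0 / 8.7 / 9.0 and the last about 7.1 / 6.2 / 7.1. The halving is itself an assumption, and acute severity not captured by pre-admission LSA would remain. The point limits the size, not the principle.

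3. **The decision rule is the F-test, which stays near 5%.** True for a uniform rise in mobility. The program is tailored to each patient, so uneven gains are plausible, and they can create a false gradient.

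4. **The weight is small.** This is one of six modifiers in a secondary aim, and sampling error is often larger than the bias. Accepted.

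5. **The dose-effect sentence covers all tertiled modifiers.** Accepted. It is context, not a separate error.

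**Conclusion.** The concern holds. Neither document defines the measure or window for this modifier. On the natural reading, the plan as written produces tertile contrasts that are not randomised comparisons and cannot show which patients to select.

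The loss of the randomised comparison needs only that the program changes in-hospital mobility. The size of any bias also needs a cause shared by mobility and LSA, and it cannot be obtained from the documents. Under the assumptions above, a uniform 10-point benefit is reported as 2.5 to 8.2 points across tertiles, and the bias is smaller with a weaker shared cause. It vanishes if there is no shared cause and no mediation. The simulations used complete data and patient means, not the full mixed model.

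The primary LSA test and the sample size are untouched. The change should be made, but the validity of the main result does not depend on it.

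**What to change.** In Aim 2 of both documents, do one of the following:

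1. **Define the modifier from a pre-session measure**, for example first-day gait speed or a first ACMA, and only where it was taken before the first study session. The protocol says "One set of assessments is to be administered on Day 1 of the study" but does not require that order. The sit-and-stand screen comes before any session, but every enrolled patient has passed it, so it cannot form tertiles.
2. **Remove mobility over the stay from the modifier list.** Report it as a process outcome, or in a separately labelled exploratory mediation or dose analysis with no randomised interpretation.

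With either option, add to Aim 2: *In-hospital mobility measured after the first study session will not be used as an effect modifier.*

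Option 1 depends on the order of measure and session having been recorded. The protocol is dated February 2021 and the ward schedules end in December 2019, so that order may not be recoverable. Option 2 is then the only one available.

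The cost is a wording change using data already specified, with one exploratory subgroup lost or relabelled. In the same edit, the timing of the depression and social-support measures should be checked. They sit in the second baseline set (Table 3), which may be completed at any point in the stay, and the sentence above does not cover them.
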